6. PRIOR AND CONCOMITANT ILLNESSES AND TREATMENTS

6.1 *Prior and Concomitant Illnesses*

Participants who have provided consent will have their files reviewed and be required to provide details to document any illnesses present at the time of sample collection. Illnesses present at the time of informed consent, will be regarded as concomitant illnesses and will be documented on the appropriate pages of the Case Report Form (CRF) - see Section 8. Adverse Events

6.2 *Prior and Concomitant Treatments*

All treatments being taken by the subjects on entry to the study or at any time during the study are regarded as concomitant treatments and must be documented preferably by generic name on the appropriate pages of the CRF.

Changes to concomitant medications should be kept to a minimum during the study. However they may be altered at the discretion of the investigator according to Good Clinical Practice.

6.3 *Prohibited medication*

A list of drugs prohibited for use during the study is listed in Appendix 2.

7. INVESTIGATIONAL PROCEDURES AND SCHEDULE

7.1 *Description of Study Schedule*

7.1.1 Visit 1 Screening and Baseline

The subject will be approached regarding the study and will be asked to read the Subject Information and Consent document, encouraged to ask any questions, which will be answered to best of the Investigators ability. If the subject agrees to participate then they will be asked to provide written informed consent. Subject will be asked to provide details of their medical history, a description of their current symptoms and list all current medications. Subjects will also be given a Diary to collect symptoms relating to coronary artery disease and this will remain with the participant for the duration of the study. The Diary will be reviewed at each visit. Blood samples will be collected for laboratory tests. Pregnancy testing will be completed to ensure pregnant women are not included into the study. The following tests and assessments will be performed:

- FBC, ESR and EUC
- LFT and Lipid Studies
- CK-MB, high sensitivity Troponin T
- High sensitivity CRP
- *Chlamydophila pneumoniae* macrophage cultures
- *C. pneumoniae* titer measurement
- *C. pneumoniae* DNA detection using LAMP

- Pregnancy Testing
- Physical examination
- Vital Signs
- Symptomatology record
- ECG
- Angiogram
- Fractional Flow Reserve Study and pressure/flow measurements
- IVUS and OCT of culprit and non-culprit arteries (sub-study)
- Functional status – New York Heart Association Class
- Concomitant medications/ concomitant illness record
- Cardiac events record

The Subject's GP will be informed of the Subjects participation in the study, unless the subject does not consent to this disclosure.

Subjects will be dispensed with investigational product with instruction on correct administration. The investigational product will be dispensed in specifically labelled bottles.

7.1.2 Visit 2 (Day 30 ± 7)

At this visit the subject will be asked to report on current symptoms, changes to concomitant medications, and adverse events. A blood sample will be collected for laboratory tests. Subject will undergo a complete physical examination. The following assessments will also be performed:

- FBC, ESR and EUC
- LFT and Lipid Studies
- CK-MB, high sensitivity Troponin T
- High sensitivity CRP
- ECG
- Physical examination
- Vital Signs
- Symptomatology record
- Functional status – New York Heart Association Class

Subjects will be required to bring their medication with them for assessment of compliance.

7.1.3 Visit 3 – End of Treatment (Day 90 ± 21)

At this visit the Subject will be asked to report on current symptoms, changes to concomitant medications, and adverse events. A blood sample will be collected for laboratory tests. Subject will undergo a physical examination. The following assessments will also be performed:

- FBC, ESR and EUC
- LFT and Lipid Studies
- CK-MB, high sensitivity Troponin T
- High sensitivity CRP
- *Chlamydophila pneumoniae* macrophage cultures
- *C. pneumoniae* titer measurement
- *C. pneumoniae* DNA detection using LAMP
- Symptomatology record
- Physical examination
- Vital Signs
- ECG
- Angiogram
- Fractional Flow Reserve Study and pressure/flow measurements
- IVUS and OCT of culprit and non-culprit arteries (sub-study)
- Functional status – New York Heart Association Class

The Subject will be required to return all unused medication, and all used empty packaging for assessment of compliance. Subjects will also be required to return diaries for review and collection.

7.1.4 Visit 4 Final Follow up

Subjects will be asked to return a final time to the clinic at Day 180 (+21 days), where changes to symptoms, concomitant medications and adverse events will be recorded.

This will mark the end of subject participation.

7.1.5 Phone Contact (Day 150)

At this time, the participant will be contacted by phone to assess symptoms and any Adverse Events after discontinuation of antibiotic therapy and to check the use of concomitant medications.

7.2 Methods of Data Collection

7.2.1 Efficacy data

Response to antibiotic therapy will be assessed through a set of specified measurements:

7.2.1.1 Laboratory Studies

Efficacy of combination therapy will be assessed using blood samples collected at each visit. The following tests will be performed: FBC, ESR, lipid studies, liver function. In addition the following will be performed:

High Sensitivity C-Reactive protein (Hs-CRP) is a protein in the blood that increases in the presence of inflammation. Hs-CRP will measure the small amounts of CRP produced by the long-term inflammation from atherosclerosis.

- 4ml of blood will be collected in an EDTA tube. This sample will then be transferred to the laboratory for a full blood count
- 4ml of blood will be collected in an SST/Gel tube and transferred to the laboratory for liver function tests, Cholesterol, triglyceride studies and hs-CRP.
- 4ml of blood will be collected in a lithium heparin tube. Sample will then be transferred to the laboratory for CK-MB, Troponin T tests and UEC testing.
- 5ml of blood will be collected in a special ESR collection tube. This will then be sent to the laboratory to test the ESR
- 2 x 4ml of blood will be collected in citrated tubes. This sample will be transferred to the laboratory for *C. pneumoniae* detection by macrophage culture and *C. pneumoniae* titer determination (Visit 1 and 3 only).
- 3 x 4ml (i.e. 12 ml) of blood will be collected in an EDTA tube. This sample will be transferred to the laboratory for *C. pneumoniae* DNA detection by LAMP (Visit 1 and 3 only).

The total blood drawn on at Visit 1 and Visit 3 will be approximately 40mls. The total blood drawn at Visit 2 will be approximately 20 ml.

Blood samples will be tested by an experienced pathologist at Lavery Pathology for all tests excluding *C. pneumoniae* DNA detection by LAMP (exploratory research) and *C.pneumoniae macrophage cultures*.

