Efficacy Data	FBC, ESR, Electrolytes/Urea/Creatine, Liver Function tests, Lipid Studies ,CK-MB, High Sensitivity Troponin T, Chlamydophila pneumoniae titer, Chlamydophila pneumoniae macrophage culture, Chlamydophila pneumoniae (c. pneumoniae) DNA detection (exploratory), hs CRP, symptomatology, Functional Status – New York Heart Association Class, Quantitative Coronary Angiography (QCA); FFR and Coronary pressure/flow indices, plaque volume, plaque composition, fibrous cap thickness, macrophage content.
Safety data	Adverse event reports, Blood tests (standard haematology, serum chemistry and pregnancy) and Physical Examination, compliance and major adverse cardiac events MACE
Statistical procedures	Results will be presented as mean +/-SD for continuous normally distributed variables, as median (interquartile range) for continuously non-normally distributed data and as percentages for categorical data. Significant changes in clinical symptom improvement, arterial flow and biochemical variables over time will be assessed using ANOVA for repeated measurements. A P value < 0.05 will be considered statistically significant.
Study duration & dates	Total of 24-month recruitment period. From Q1 - 2018 to Q3 - 2019. Study duration is 6 months from the initial angiographic procedure

PATIENT FLOW DIAGRAM

STUDY SCHEDULE

Assessments and Recordings	V1	V2	Phone Call	V3	Phone Call	Phone Call	V4
	Screening and Baseline	Day 30 (+7 days)	Day 60	Day 90 (+21 days)	Day 120	Day 150	Day 180 (+ 21 days)
Subject Information	X						
Informed Consent	X						
Inclusion/Exclusion Criteria	X						
Demographics	X						
Medical History	X						
Confirmation of eligibility	X						
Laboratory tests							
FBC	X	X		X			
ESR	X	X		X			
EUC	X	X		X			
Liver Function Tests	X	X		X			
Lipid Studies	X	X		X			
CK-MB	X	X		X			
High Sensitivity Troponin T	X	X		X			
High Sensitivity CRP	X	X		X			
Pregnancy testing	X						
C. pneumoniae macrophage cultures	X			X			
C. pneumoniae titers	X			X			
C. pneumoniae DNA detection	X			X			
Physical Examination	X	X		X			
Vital Signs	X	X		X			
Quantitative Coronary Angiogram	X			X			
ECG	X			X			
New York Heart Association Functional Class	X	X		X			
Fractional Flow Reserve, Pressure/flow wire measurements and intracoronary imaging (IVUS + OCT)	X			X			
Concomitant medications	X	X	X	X	X	X	X
Concomitant illnesses	X	X	X	X	X	X	X

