In subjects with stable coronary heart disease (CHD) and inducible ischemia, percutaneous coronary interventions (PCI) can improve symptoms. As coronary angiography is often inexact in accurately determining the functional significance of non-critical coronary stenoses, fractional flow reserve (FFR) can assess their physiological significance¹². For subjects with acute coronary syndromes and multivessel disease undergoing an early invasive strategy, performing PCI in the culprit vessel and 'staging' possible treatment allows measurement of non culprit FFR at initial angiography. While non-culprit FFR in Acute Coronary Syndrome (ACS) subjects may worsen acutely due to endothelial dysfunction, randomisation should minimise confounding. Return for planned staged PCI as guided by angiography has been standard practice in such subjects, and increasingly, revascularisation is FFR guided. We plan to perform another FFR study to evaluate flow changes over a three month period.

The coronary circulation is comprised of two major components: the major epicardial coronary arteries which have a capacitance function; and the microvascular circulation comprised of pre-arterioles and arterioles which provide a metabolic interface with cardiac myocytes.¹³ Both components of the circulation have been implicated in coronary ischaemia. By measuring pressure and flow in the epicardial coronary artery, indices to assess the microcirculation can be calculated such as CFR, IMR, HSR, HMR at the same time as calculating the FFR value. This provides a comprehensive physiological assessment of the entire coronary circulation¹⁴. We plan to record pressure and flow indices at the time of measurement of FFR in the culprit and non-culprit arteries.

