4. SELECTION OF STUDY POPULATION

4.1 Inclusion Criteria

The subject must meet all of the following criteria to be eligible for inclusion in the study:

1. Males and females (without childbearing potential as evidenced by hysterectomy, tubal ligation or at least one year post-menopause) aged 18 to 80 years, inclusive.
2. Ability to provide written informed consent to participate in the study.
3. Subjects with documented recent acute coronary syndrome (ACS) or evidence of myocardial ischemia.
4. Subjects who have a culprit lesion suitable for PCI, and a non-critical lesion in another vessel suitable for staged PCI with an FFR of ≤ 0.80 , for subjects undergoing diagnostic angiography and FFR without ad hoc PCI. Or subjects who have a single non-critical culprit lesion of intermediate severity with a clinically indicated FFR ≤ 0.80 which is suitable for staged PCI.
5. No serious co-morbidities, which might interfere with the subject's ability to enter the study.
6. Able to communicate effectively with the study team and to comply with the protocol.

4.2 **Exclusion Criteria**

The subject must be excluded for any of the following reasons:

1. Females that are of child bearing potential
2. Subjects without a non-culprit lesion considered appropriate to plan a staged PCI.
3. Clinically significant haematologic, hepatic, metabolic, renal, rheumatologic, anaphylactic reactions, neurological or psychiatric disease
4. Clinical evidence of any other disease, which might interfere with the subject's ability to enter the trial.
5. Concomitant administration of medications that may interfere with treatment as assessed by the Investigator, including allergy to any component of the therapy.
6. Concomitant administration of any medication prohibited for use during this study (e.g. colchicine)
7. Male subjects consuming greater than 60g alcohol per day, or female subjects consuming greater than 40g alcohol per day.
8. Evidence of any recent history of, or current recreational drug abuse
9. Serious adverse reaction or hypersensitivity to therapeutic drugs.
10. Unable and to comply with the study requirements.
11. Subjects who have been involved in an experimental drug protocol within the past four weeks.

A list of subjects screened but deemed ineligible will be maintained indicating reason(s) for exclusion.

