11. STATISTICAL PROCEDURES

11.1 *Analysis Variables*

Analysis of efficacy will be performed according to intention-to-treat method and include all subjects who received the combination antibiotic therapy. However as the primary efficacy analysis is of subjects with paired FFR assessments, only such subjects will be included in the primary analysis. All other subjects will be included in secondary analyses. Numerical data will be presented as mean \pm SD for normally distributed variables and as median with interquartile range for non-normally distributed data. Non-normally distributed data will be log-transformed (e.g. CRP levels) before being used for comparisons. Significant changes in subjects' arterial flow, clinical symptoms and biochemical variables over time compared with that baseline will be assessed using an analysis of covariance. Differences between treatment and control groups in the occurrence of FFR \geq 80 will be assessed using Fisher's exact test. All tests will be 2-tailed with a 5% significance level.

11.2 *Interim Analysis*

A DSMB directed interim analysis is planned when 60 paired FFR data are available. At this time point, the trial would declare the combination therapy as effective if the p value is less than 0.05. However, the trial might still continue to collect extra data to accurately characterise side effects as advised by the DSMB.

11.3 *Sample Size Justification*

This is a feasibility study designed to provide preliminary observations and generate hypothesis for future studies. The sample size of 60 subjects with paired FFR was not defined on the basis of a clinical endpoint hypothesis but rather to provide information about antibiotic combination therapy efficacy and safety. The sample size required is established by assessment of the minimum number of subjects needed to provide reliable and non-trivial results. The sample size is in the range of the intervention group in the azithromycin clinical trial of subjects with CAD (n=60).

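### In recent-ACS entrants, Visit 1 hs-CRP, ESR, CK-MB and troponin may reflect the acute event or index procedure, so change from Visit 1 is not evidence of efficacy; yet the plan tests that change and names no between-arm contrast

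*Combined protocol and SAP*

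**What the plan says.** - **Role of the markers.** The Efficacy Data row of the protocol synopsis includes "FBC, ESR, Electrolytes/Urea/Creatine, Liver Function tests, Lipid Studies ,CK-MB, High Sensitivity Troponin T" and, later in the row, "hs CRP, symptomatology, Functional Status". Section 7.2.1.1 opens: "Efficacy of combination therapy will be assessed using blood samples collected at each visit".
- **What hs-CRP is said to show.** "Hs-CRP will measure the small amounts of CRP produced by the long-term inflammation from atherosclerosis" (section 7.2.1.1). Nothing similar is said of ESR, CK-MB or troponin.
- **Who enters.** "Subjects with documented recent acute coronary syndrome (ACS) or evidence of myocardial ischemia" (section 4.1). How recent the ACS must be is not defined. The same section also admits subjects who have diagnostic angiography without PCI at that sitting.
- **When baseline is taken.** The study schedule and section 7.1.1 combine screening, baseline blood, angiogram and FFR in Visit 1. Section 1.1 explains that in ACS with multivessel disease, treating the culprit vessel and staging the rest "allows measurement of non culprit FFR at initial angiography". Sections 7.1.1 and 7.1.3 mention blood before the angiogram but set no order, and no interval from the event or from PCI.
- **Analysis.** The synopsis assesses change in biochemical variables over time by repeated-measures ANOVA. Section 11.1 says that "biochemical variables over time compared with that baseline will be assessed using an analysis of covariance". The only between-group test it names, Fisher's exact test, is for FFR.

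**The concern.** A subject sampled within days of an ACS, or just after culprit PCI, may have hs-CRP and ESR raised by the acute response and CK-MB and troponin raised by myocardial injury. These values would be expected to fall by Day 30 or Day 90 on either treatment. The plan tests change since that sample and does not say that the quantity of interest is the difference between arms.

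Two other passages make a within-arm reading easier. Section 11.1 describes the efficacy set as subjects who received the antibiotic combination. Section 7.2.2.1 uses a pre/post comparison of *C. pneumoniae* parameters to show efficacy.

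Visit 3 raises a related question. It is the planned staged-PCI visit, and section 1.1 notes that revascularisation is increasingly guided by FFR. If blood were drawn after PCI, CK-MB and troponin could differ between arms only because Visit 3 FFR, the primary outcome, differed.

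At stake is the supporting anti-inflammatory evidence, not the primary result.

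**Working it through.** **1. The plan's own figure.** No effect size or power is given for any biomarker. The one derived number is the 80 subjects to be approached: 60/(1 − 0.25) = 80, which reproduces. With 1:1 allocation, 60/2 = 30 per arm have paired data.

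**2. Inputs.**
- From the documents: 30 per arm; two-sided 5% level and log-transformed CRP (section 11.1); Visit 1 as baseline.
- Assumed, because the documents do not give them: ACS share *p* from 30% to 70%; acute rise of 2- to 5-fold in ACS entrants, with log-SD 0.7, gone by follow-up; log hs-CRP between-subject SD 0.9 and within-subject SD 0.5; no drug effect.

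**3. Change within the placebo arm.** Let L = ln(fold rise).
- Mean fall on the log scale = pL.
- Variance of a subject's change = 2(0.25) + 0.49p + p(1 − p)L².
- z = pL / √(variance/30).
- Chance of p < 0.05 ≈ Φ(z − 2.045), where 2.045 is the t critical value on 29 df.

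Example, p = 0.5 and 2-fold: L = 0.693, fall = 0.347 (geometric mean down 29%), variance = 0.5 + 0.245 + 0.120 = 0.865, z = 0.347/0.170 = 2.04, chance about 50%.

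| ACS share | Rise | Fall in geometric mean | z | Significant fall, no drug effect |
|---|---|---|---|---|
| 30% | 2-fold | 19% | 1.32 | 23% |
| 30% | 5-fold | 38% | 2.42 | 65% |
| 50% | 2-fold | 29% | 2.04 | 50% |
| 50% | 5-fold | 55% | 3.74 | 95% |
| 70% | 2-fold | 38% | 2.74 | 75% |
| 70% | 5-fold | 68% | 5.24 | 100% |

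Simulation (3,000 trials per setting) agrees to within about two percentage points. A second simulation with other assumptions (SD 1.0, correlation 0.5, a fixed rise) gave 14–40% at 25% ACS, 40–92% at 50% and about 5% with no ACS entrants.

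**4. Comparison between arms.** In that second simulation, ANCOVA of the follow-up value on arm and baseline rejected in 4.5–5.7% of null trials in every scenario. Both arms share the recovery, so it cancels. With an assumed 40% drug reduction, ANCOVA power was 59–61% with no ACS entrants and 53–59% at 50% ACS. An unadjusted comparison of change scores fell from 48–50% to 24–44%.

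**5. Precision gained from ACS status.** Follow-up variance is 0.81 + 0.25 = 1.06, and its covariance with baseline is 0.81.
- Residual variance, baseline only: 1.06 − 0.81²/[1.06 + 0.49p + p(1 − p)L²].
- Residual variance, baseline plus ACS: 1.06 − 0.81²/[1.06 + 0.49p].

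At p = 0.5 and 5-fold: 1.06 − 0.656/1.953 = 0.724 against 1.06 − 0.656/1.305 = 0.557, a ratio of 1.30. At p = 0.5 and 2-fold: 1.06 − 0.656/1.425 = 0.600 against 0.557, a ratio of 1.08. Simulation at 30 per arm over the whole grid puts the extra subjects needed when ACS status is left out at about 3–34%; as a saving from including it, 1 − 1/1.34 = 25% at most. A baseline-by-ACS product term adds almost nothing: at 50% ACS and 5-fold the SE is 0.194 with it and 0.195 without.

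**6. CK-MB, troponin and ESR.** No arithmetic was done for these. The argument for them rests on the passages: they are listed as efficacy data, the draw is not ordered against catheterisation at Visit 1 or Visit 3, and no passage says what a change in CK-MB or troponin would mean for efficacy.

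**The case against.** The strongest reply is that the trial is randomised, double-blind and placebo-controlled, so any recovery appears in both arms. Section 11.1 names analysis of covariance, and step 4 shows that, used between arms, it keeps its 5% error. A reader might infer that the acute baseline biases the treatment comparison; it does not. What remains is that neither the synopsis nor section 11.1 says the biomarker model compares arms.

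A reader might also infer that every baseline is taken at an acute event and that change mostly shows ACS recovery. The documents do not support that. Subjects with ischaemia but no ACS may enter, some have no PCI at the index angiogram, and the ACS share, the interval and the draw order are not stated. Nor does the plan claim that all four markers measure plaque inflammation; that sentence concerns hs-CRP only.

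The Visit 3 point is conditional: it needs blood drawn after PCI, which the documents neither state nor exclude.

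Finally, the stakes are low. No listed objective names these markers, the Efficacy Data row also holds routine tests, section 7.2.2.1 already treats these bloods as safety data, and section 11.3 calls this a feasibility study. All of that stands. It limits the weight of the point, but does not make a fall from Visit 1 interpretable.

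**Conclusion.** The point holds in limited form. For subjects entering with recent ACS, Visit 1 hs-CRP, ESR, CK-MB and troponin cannot be assumed to be free of the acute event or procedure, so change from Visit 1 is not evidence of efficacy. The plan as written assesses that change and names no contrast between arms.

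Under the assumed ranges, a within-placebo change test on hs-CRP would be significant in about 23–100% of trials with no drug effect. The range is wide because the ACS share and the acute rise are unknown; with no ACS entrants the rate is about 5%. A between-arm ANCOVA is valid either way. Leaving out ACS status costs precision equal to about 3–34% more subjects, and the upper end needs a 5-fold rise. The primary FFR analysis is not touched. This is a cheap improvement to supportive endpoints, not a threat to the trial's main conclusion.

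**What to change.** - **Section 11.1 and synopsis:** compare arms at Visits 2 and 3 on the log scale by ANCOVA, with baseline value and ACS at entry as covariates. No product term is needed. State that no efficacy conclusion is drawn from within-group change.
- **Sections 7.1.1, 7.1.3 and 7.2.1.1:** draw Visit 1 and Visit 3 blood before the catheter procedure, and record the time from ACS onset and from any PCI. Visit 3 enzymes then cannot reflect PCI done at that visit in response to FFR.
- **Synopsis and section 7.2.1.1:** report CK-MB and troponin as safety data, and limit the hs-CRP sentence to samples not taken in the acute phase.

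Cost: a task-order rule within two existing visits, a timing entry on the CRF and one model term. No new visit, sample or subject is needed. The efficacy list becomes two markers shorter.
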